11.1 Extent of exposure

11.1.1 Drug administration

All drug administration details (including date, time of injection, location, side of body and volume delivered) will be listed. The IMP will be given as 2 sc injections at each planned dosing visit (Baseline, Week 4 and Week 16).

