11.1.3 Subject time at risk

The subject time at risk represents the time a subject was at risk for having an AE and will be used to calculate the exposure adjusted incidence rate (EAIR) and exposure adjusted event rate (EAER) as described in [Section 11.2](#).

The subject time at risk (days) will be calculated as follows:

$$\text{Time at risk} = (\text{Date of Last Dose} - \text{Date of First Dose}) + 140 \quad [11]$$

In cases where the last clinical contact or last visit occurs prior to completion of the SFU period, the subject time at risk is calculated as follows:

$$\text{Time at risk} = (\text{Date of Last Contact} - \text{Date of First Dose}) + 1 \quad [12]$$

This will apply for the following:

- For subjects entering the extension study the date of last contact (in PS0016) refers to the date of the visit at which they enter the extension study (ie, Week 20, 24, 28 or 36)
- For subjects that discontinue prematurely (ie, and no SFU data are available), the date of final contact refers to the date of the latest contact with the subject during the study after

which no further information or data are available. This will be reported on the study termination page of the CRF.

- For subjects that have died during the study the date of last contact refers to the date of death
- Subject-years at risk is defined as the subject time at risk divided by 365.25. The days at risk and subject-years at risk will be listed together with the drug administration information (Section 11.1.1).

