 - Incidence of TEAEs (including all TEAEs during Treatment and Post-Treatment Periods) by SOC, HLT and PT and including the EAIR and EAER, stratified by overall ADA status (positive/negative)

In addition, separate AE summaries by treatment group, SOC, HLT and PT (including all TEAEs during Treatment and Post-Treatment Periods combined) will be included for the following AEs of special monitoring (AESM):

- Major cardiovascular events
- Serious infections, including opportunistic infections and tuberculosis (TB)
- Malignancies including lymphoma

- Cytopenias
- Neuropsychiatric events (in particular, depression and suicide)
- Inflammatory bowel disease
- Anaphylactic reaction (hypersensitivity and anaphylactic reactions)
- Hepatic events and drug-induced liver injury

All summary tables (including those for AESM) will contain the number and percentage of subjects and the number of events where applicable. A subject who has multiple events in the same SOC, HLT and PT will be counted only once in the subject counts but all events will be included. In addition, for all tabulations of AESM, the EAER and EAIR will be reported.

The criteria for identifying AESM and additional criteria for reporting AESM are provided in [Section 14.6](#).

In summaries including relationship to IMP, the following relationship categories will be included:

- Related
- Not related

Subjects who experience the same event multiple times will be included in the most related category for tabulations by maximum relationship. Events with missing relationship will be considered as 'Related' for summary purposes but shown as missing in the data listings.

In summaries including intensity, the following categories will be summarized:

- Mild
- Moderate
- Severe

Subjects who experience the same event multiple times will be included in the most severe category for tabulations by maximum intensity. Events with missing intensity will be considered as severe for summary purposes. All data will be presented as recorded in the database for the listings.

Adverse event summaries will be ordered by alphabetical SOC, alphabetical HLT within SOC and decreasing frequency of PT in the 'BKZ 320mg' (Treatment arm B) column for tables including event counts. For tables including only number and percentage of subjects, summaries will be ordered by alphabetical SOC, alphabetical HLT within SOC and decreasing incidence of PT within HLT and SOC in the 'BKZ 320mg' (Treatment arm B) column.

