14.6 Adverse events of special monitoring

The following AESM are defined for bimekizumab and will be summarized separately as described in [Section 11.2](#):

- Major cardiovascular events
- Serious infections, including opportunistic infections and TB

- Malignancies including lymphoma
- Cytopenias
- Neuropsychiatric events (in particular, depression and suicide)
- Inflammatory bowel disease
- Anaphylactic reaction (hypersensitivity and anaphylactic reactions)
- Hepatic events and drug-induced liver injury

All AESM tabulations will be presented by treatment group, SOC, HLT and PT, based on the SS, and will include the EAIR and EAER.

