14.6.7 Anaphylactic reaction

Anaphylactic reactions will be summarized together in a stand-alone table with the following incidence rows:

- The first row within the body of the table will be labeled ‘Any hypersensitivity/anaphylactic reaction’ and will represent the overall incidence of subjects who reported at least one hypersensitivity reaction or at least one anaphylactic reaction.
- The second row within the body of the table will be labeled ‘Any hypersensitivity reaction’ and will represent the overall incidence of subjects who reported at least one hypersensitivity reaction.
- The third row within the body of the table will be labeled ‘Any anaphylactic reaction’ and will represent the overall incidence of subjects who reported at least one anaphylactic reaction.

Following these three overall incidence rows, all TEAEs that have been identified as either a hypersensitivity reaction or an anaphylactic reaction will be summarized by SOC, HLT and PT (these will not be presented by subcategory).

Hypersensitivity reactions and anaphylactic reactions will be identified as follows:

- **Hypersensitivity reactions:** all TEAEs with onset (start date/time) within 24 hours after any administration of IMP, which code to a PT which contains the term ‘hypersensitivity’ will be considered to be a hypersensitivity reaction and included in the summary table
- **Anaphylactic reactions:** An algorithmic approach will be used to identify TEAEs that are considered to be anaphylactic reactions. Preferred terms are separated into 4 distinct categories (A, B, C, D) prior to the algorithmic approach being applied.

All TEAEs with onset (start date/time) within 24 hours after any administration of IMP, and which fulfill any of the 3 criteria described in [Section 14.6.7.1](#) will be included in the summary table.

Any TEAEs with missing start time will be assumed to have occurred at the time of or after dosing for this purpose, if the event date is on the same day as a dosing date.

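### SAP 14.6.7 counts reactions only within 24 hours of dosing, but their EAIR and EAER use the whole follow-up as time at risk, so the rates depend on when subjects leave

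*SAP*

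**What the plan says.** **Numerator.** SAP 14.6.7 applies the same 24-hour limit to both event types. Hypersensitivity reactions are "all TEAEs with onset (start date/time) within 24 hours after any administration of IMP, which code to a PT which contains the term" hypersensitivity. Anaphylactic reactions are "All TEAEs with onset (start date/time) within 24 hours after any administration of IMP, and which fulfill any of the 3 criteria" of the algorithm. For a missing clock time the rule is "Any TEAEs with missing start time will be assumed to have occurred at the time of or after dosing for this purpose", provided the event falls on a dosing date, so the count stays tied to dosing.

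**Rates required.** SAP 11.2.3 says that "for all tabulations of AESM, the EAER and EAIR will be reported". SAP 14.6 lists hypersensitivity and anaphylactic reactions among the AESM and adds: "All AESM tabulations will be presented by treatment group, SOC, HLT and PT, based on the SS, and will include the EAIR and EAER". Nothing in 14.6.7 exempts this table or gives it its own denominator.

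**Denominator.** SAP 11.1.3 states that "The subject time at risk represents the time a subject was at risk for having an AE". Equation 11 sets it to the first-to-last-dose interval plus 140 days. Equation 12 ends it at the last contact, which for an extension entrant is the visit of entry. SAP 11.2.2 uses this time for every subject in the EAER and for event-free subjects in the EAIR. In the EAIR, a subject with the event contributes only the time from first dose to first onset.

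**Dosing.** SAP 11.1.1 plans dosing at Baseline, Week 4 and Week 16 in both arms. At Week 16, Arm A receives placebo and Arm B bimekizumab (SAP 2.3).

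**The concern.** An exposure-adjusted rate means something when events could have been counted during the exposure time. Here almost none of that time qualifies. After the third 24-hour window closes at about Week 16, each further day of follow-up enlarges the denominator and cannot add to the numerator.

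That extra time is not neutral. From Week 20, previous PASI25 responders who relapse may move to the extension study, which ends their time at risk in this study. A subject who leaves at Week 20 has had the same three dosing visits as one followed to Week 36, but contributes (252 - 141)/252 = 44% less time. Two arms with the same reaction risk per dosing visit can therefore show different rates because they relapse at different speeds.

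SAP 11.2.1 excuses the EAIR and EAER from the Week 20 cut-off on the ground that they already adjust for each subject's exposure at risk. For this table that ground does not hold. No other AESM definition in SAP 14.6 restricts onset to a post-dose window, so the problem is confined to this table.

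**Working it through.** **Inputs**
- Countable window: 24 hours per administration (SAP 14.6.7); three dosing visits, so 3 days.
- Nominal dosing times: 0, 28 and 112 days after the first dose (SAP 11.1.1).
- Time at risk: equations 11 and 12 (SAP 11.1.3). Rates: equations 13 and 15 (SAP 11.2.2).
- Arm sizes: about 30 (A) and 15 (B) (SAP 2.3).
- Assumed, not in the documents: the number of reactions, and the fraction *f* of Arm A entering the extension at Week 20.

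**1. The plan's own timeline.** Screening 4 weeks + 16 weeks to the last dose + 20 weeks of follow-up = 40 weeks, the maximum stated in SAP 3.2.1.2. Equation 11 gives 112 + 140 = 252 days, which is the 36 weeks after screening. The two agree.

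**2. Time at risk for a three-dose subject**

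| Leaves at | Time at risk (days) | Countable share | Not countable |
|---|---|---|---|
| Week 20 (eq. 12) | 140 + 1 = 141 | 3/141 = 2.1% | 97.9% |
| Week 24 (eq. 12) | 168 + 1 = 169 | 3/169 = 1.8% | 98.2% |
| Week 28 (eq. 12) | 196 + 1 = 197 | 3/197 = 1.5% | 98.5% |
| Full follow-up (eq. 11) | 252 | 3/252 = 1.2% | 98.8% |

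**3. Upper bound on the arm difference.** At equal reactions per subject, the EAER is inversely proportional to mean time at risk. If everyone in one arm left at Week 20 and everyone in the other completed, the ratio would be 252/141 = 1.79. The ±3-day visit window moves 141 to 138-144, giving 252/144 = 1.75 to 252/138 = 1.83.

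**4. Illustration at identical risk.** Take 2 reactions in 30 × 3 = 90 dosing visits in Arm A and 1 in 15 × 3 = 45 in Arm B, which is 2.2 per 100 dosing visits in both. Arm B with full follow-up: 15 × 252/365.25 = 10.35 subject-years, so EAER = 100 × 1/10.35 = 9.66 per 100 subject-years. Arm A has mean time 141*f* + 252(1 - *f*):

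| *f* | Mean days | Subject-years | EAER, Arm A | Ratio A/B |
|---|---|---|---|---|
| 0 | 252 | 20.70 | 9.66 | 1.00 |
| 0.20 | 229.8 | 18.87 | 10.60 | 1.10 |
| 0.25 | 224.25 | 18.42 | 10.86 | 1.12 |
| 0.50 | 196.5 | 16.14 | 12.39 | 1.28 |

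If 10% of Arm B also left at Week 20, its mean would be 240.9 days, and the ratio at *f* = 0.50 would be 240.9/196.5 = 1.23.

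**5. EAIR.** Stopping at first onset does not remove the dependence, because event-free subjects dominate the denominator. With one first-dose reaction (1 day at risk) among 15 subjects:
- all others complete: (1 + 14 × 252)/365.25 = 9.66 subject-years, EAIR 10.35;
- all others leave at Week 20: (1 + 14 × 141)/365.25 = 5.41 subject-years, EAIR 18.49.

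The ratio is again 1.79.

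**6. Alternative.** Reactions per 100 dosing visits stays at 2.2 in both arms of step 4 for every value of *f*.

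**The case against.** **Much is already in place.** SAP 11.2.3 puts subject counts, percentages and event counts in every AESM table, and the three lead rows in 14.6.7 are subject incidences. These do not use the denominator. The Treatment Period TEAE tables, cut at Week 20, cover all three dosing visits on a common window, though without the 24-hour filter. This stands and lowers the stakes. It does not change what the EAIR and EAER columns show.

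**The rate is well defined.** The EAER can be read as post-dose reactions per 100 subject-years of follow-up. That is true, but it is not the exposure-adjusted rate that SAP 11.2.1 describes.

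**The arm difference is hypothetical.** It needs assumed events and leaving fractions. Later leavers shrink it. One event in 10.35 subject-years has an exact Poisson 95% interval (equation 14) of about 0.2 to 54 per 100 subject-years, so a shift of 10-28% is small beside chance. Equal risk per dosing visit is itself doubtful, since 30 of Arm A's 90 planned dosing visits are placebo. All of this stands.

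**Two stronger readings are not supported.**
- A reader might divide 252 and 141 by 3 and say the rates are diluted 84- or 47-fold. That compares the planned rate with one per unit of window time, which the SAP does not plan and which is not proposed here. The range also holds only for three-dose subjects who stay to at least Week 20. One dose with full follow-up gives 140/1 = 140; one dose with last contact on Day 15 gives 15/1 = 15.
- A reader might infer that Arm A's rate will be inflated because its last active dose is at Week 4. The documents give no relapse or extension-entry fractions by arm, and relapse means falling below PASI25 after reaching it, which is a demanding threshold. The direction is plausible but not established.

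**Conclusion.** The mismatch is real and follows from the SAP's own text: the numerator is confined to about 3 days per fully dosed subject, while the required rates use 141 to 252 days. The EAER takes the whole follow-up for everyone; the EAIR does so for event-free subjects. The rates therefore vary with departure after Week 16, at unchanged reaction risk.

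The 1.79-fold bound applies to three-dose subjects who stay to at least Week 20, at nominal visit days. The 1.10-1.28 range is illustrative and rests on 20-50% of Arm A and none of Arm B leaving at Week 20, with equal risk at every dosing visit.

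The consequence is limited. The study is exploratory and not powered for conclusions on safety (SAP 2.4). No test or decision rule depends on these columns, and the primary safety variable is AE incidence. The correction is worth making because it is cheap and the columns would otherwise be read as risk rates.

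**What to change.** In SAP 14.6.7, state that the EAIR and EAER requirement of 11.2.3 and 14.6 does not apply to the hypersensitivity and anaphylactic reaction table. Keep the planned n (%) and event counts. Add the number of reactions per 100 dosing visits, with dosing visits (two injections each) as the denominator, shown by product injected (bimekizumab or placebo). Assign each reaction to the dosing visit whose 24-hour window contains it. Protocol 7.2 sets at least 24 days between doses, so the windows cannot overlap.

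The split by product matters because Arm A's Week 16 dose is placebo, which an arm-level figure would hide.

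Cost: one SAP sentence and one table shell, using dosing data already listed under SAP 11.1.1. The small downside is that this table leaves the per-100-subject-year scale shared by the other AESM tables.

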14.6.7.1 Anaphylactic reaction algorithm

The SMQ = ‘anaphylactic reaction’ consists of 3 parts:

- A **narrow search** containing PTs that represent core anaphylactic reaction terms. If a subject reports any TEAE which codes to a PT included in Category A, then the event will be flagged as an anaphylactic reaction and summarized as such in the table.

– Category A

1. Anaphylactic reaction
2. Anaphylactic shock
3. Anaphylactic transfusion reaction
4. Anaphylactoid reaction
5. Anaphylactoid shock
6. Circulatory collapse
7. Dialysis membrane reaction
8. Kounis syndrome
9. Shock
10. Shock symptom
11. Type I hypersensitivity

- A **broad search:** If a subject reports any TEAE which codes to a PT included in Category B **AND** reports any TEAE which codes to a PT included in Category C, **and both TEAEs have the same start date**, then both events will be flagged as anaphylactic reactions and summarized as such in the table.

– Category B

1. Acute respiratory failure
2. Asthma
3. Bronchial oedema

4. Bronchospasm
5. Cardio-respiratory distress
6. Chest discomfort
7. Choking
8. Choking sensation
9. Circumoral oedema
10. Cough
11. Cyanosis
12. Dyspnoea
13. Hyperventilation
14. Irregular breathing
15. Laryngeal dyspnoea
16. Laryngeal oedema
17. Laryngospasm
18. Laryngotracheal oedema
19. Mouth swelling
20. Nasal obstruction
21. Oedema mouth
22. Oropharyngeal spasm
23. Oropharyngeal swelling
24. Respiratory arrest
25. Respiratory distress
26. Respiratory dyskinesia
27. Respiratory failure
28. Reversible airways obstruction
29. Sensation of foreign body
30. Sneezing
31. Stridor
32. Swollen tongue
33. Tachypnoea
34. Throat tightness
35. Tongue oedema
36. Tracheal obstruction

-
- 37. Tracheal oedema
 - 38. Upper airway obstruction
 - 39. Wheezing

– **Category C**

- 1. Allergic oedema
- 2. Angioedema
- 3. Erythema
- 4. Eye oedema
- 5. Eye pruritis
- 6. Eye swelling
- 7. Eyelid oedema
- 8. Face oedema
- 9. Flushing
- 10. Generalised erythema
- 11. Injection site urticaria
- 12. Lip oedema
- 13. Lip swelling
- 14. Nodular rash
- 15. Ocular hyperaemia
- 16. Oedema
- 17. Periorbital oedema
- 18. Pruritis
- 19. Pruritis allergic
- 20. Pruritis generalised
- 21. Rash
- 22. Rash erythematous
- 23. Rash generalized
- 24. Rash pruritic
- 25. Skin swelling
- 26. Swelling
- 27. Swelling face
- 28. Urticaria

29. Urticaria papular

– **Category D**

1. Blood pressure decreased
2. Blood pressure diastolic decreased
3. Blood pressure systolic decreased
4. Cardiac arrest
5. Cardio-respiratory arrest
6. Cardiovascular insufficiency
7. Diastolic hypertension
8. Hypotension

- An **algorithmic approach**: If a subject reports any TEAE which codes to a PT included in Category D **AND** reports (either a TEAE which codes to a PT included in Category B **OR** a TEAE which codes to a PT included in Category C), **and both TEAEs have the same start date**, then both events will be flagged as anaphylactic reactions and summarized as such in the table.

14.6.8 Hepatic events and drug-induced liver injury

Hepatic events will include:

- Events based on the SMQ = ‘Drug related hepatic disorders – comprehensive search’ (excluding sub-SMQs = ‘Liver neoplasms, benign [incl cysts and polyps]’ and ‘Liver neoplasms, malignant and unspecified’). All AEs should be included in the tabulation (included those considered both related and not related to the IMP) which code to a PT included in the Scope=Narrow group within each SMQ.
- Hy’s Law cases will also be summarized separately in a table of liver function abnormalities as described in [Section 11.3](#) (with adjudication for potential drug-induced liver injury cases).

14.7 Treatment-emergent markedly abnormal vital signs values

The criteria for identifying TEMA/PCS vital signs values are provided in [Table 14-6](#).

Table 14-6: TEMA/PCS criteria for vital signs

Variable	Unit	Low ^a	High ^a
Systolic blood pressure	mmHg	Value ≤ 90 and ≥ 20 decrease from Baseline	Value ≥ 180 and ≥ 20 increase from Baseline
Diastolic blood pressure	mmHg	Value ≤ 50 and ≥ 15 decrease from Baseline	Value ≥ 105 and ≥ 15 increase from Baseline

Note: the change in measurement (increase or decrease) will be calculated relative to the value obtained at Baseline.

^a Both conditions must be satisfied for a measurement to be considered TEMA/PCS.

15 AMENDMENTS TO THE SAP

15.1 Rationale for the amendment

Amendment 1 for this SAP was primarily created to add the extra tables and figures that were generated for Interim Analysis 3. In addition, the SAP focuses on the percentage change in PASI score from Baseline rather than the percentage improvement, to recognize the possibility that the change may be worsening.

15.2 List of changes

Change #1: Introduction, 2nd paragraph

This SAP Amendment 1 is based on, and assumes familiarity, with the following documents:

- Final protocol, dated 06 June 2016
- Protocol amendment 1, dated 04 August 2016
- Protocol amendment 2, dated 06 September 2016
- Protocol amendment 3, dated 23 September 2016

The following bullet has been added:

- Statistical analysis plan, dated 23 February 2017

Change #2: Section 4.3

The following bullet has been added:-

- Data from unscheduled visits may be used for tables that present abnormalities (where stated in the SAP amendment).

Change #3: Section 4.5.2

No formal interim analysis will be performed; however data cuts will be performed and evaluated.

Has been changed to:-

No formal interim analysis will be performed; however interim data cuts will be performed and evaluated.

Change #4: Section 8.1.1

Improvement from Baseline = $100x[(Baseline\ PASI - PostBaseline\ PASI)/Baseline\ PASI]$
[9]

Has been changed to:-

Percentage improvement from Baseline = $100x[(PostBaseline\ PASI - Baseline\ PASI)/Baseline\ PASI]$ [9]

Change #5: Section 8.1.2, 4th paragraph

All tabulations and both individual and mean figures will be presented using the FAS and repeated for the PPS.

Has been changed to:-

All tabulations and both individual and mean figures will be presented using the FAS and repeated for the PPS (only if the PPS differs from the FAS).

Change #6: Section 8.1.2, final paragraph

Tabulations (absolute values and percentage improvement from Baseline) will also be repeated using observed cases, based on the FAS only.

Has been changed to:-

Separate tables and mean figures will also be created based on the observed cases only.

Change #7: Section 8.2.1, 3rd paragraph

Missing data will be imputed using NRI as described in [Section 4.2.1.1](#). Subjects with missing data at Week 16 will be regarded as nonresponders for the PASI75, PASI90, and PASI100 variables. Missing data will not be imputed for the listing.

Has been changed to:-

Missing data will be imputed using NRI as described in [Section 4.2.1.1](#). Subjects with missing data at Week 16 will be regarded as nonresponders for the PASI75, PASI90, and PASI100 variables. This will also be presented using observed cases. Missing data will not be imputed for the listing.

Change #8: Section 8.3.1, 6th paragraph deleted

The tabulation will also be repeated using observed cases and will include a category for missing data;

Change #9: Section 8.3.1, 5th paragraph:

Has been added

The tables and figures for PASI response variables will also be repeated using observed cases and will include a category for missing data;

Change #10: Section 8.3.2, 2nd paragraph

This sentence has been added:-

The percentage of responders (with 95% CI) will also be plotted over time.

Change #11: Section 8.3.2, 3rd paragraph

The tabulation will also be repeated using observed cases

Has been changed to:-

The table and figure will also be repeated using observed cases

Change #12: Section 11.2.3

In addition, the following summaries will be presented by treatment group, SOC, high level term (HLT) and PT, based on the SS:

- Incidence of TEAEs during Treatment Period
- Incidence of TEAEs during Post-Treatment Period
- Incidence of serious TEAEs during Treatment Period
- Incidence of serious TEAEs during Post-Treatment Period
- Incidence of non-serious TEAEs during Treatment Period
- Incidence of TEAEs during Treatment Period by relationship
- Incidence of TEAEs during Treatment Period by maximum relationship
- Incidence of TEAEs during Treatment Period by maximum intensity
- Incidence of fatal TEAEs during Treatment Period by relationship
- Incidence of non-serious TEAEs during Treatment Period by relationship
- Incidence of serious TEAEs during Treatment Period by relationship
- Incidence of non-serious TEAEs during Treatment Period above threshold of 5% of subjects
- Incidence of non-serious TEAEs during Treatment Period above threshold of 5% of subjects by relationship
- Incidence of TEAEs during Treatment Period by SOC and PT (including the number and percentage of subjects and individual subject numbers/reported terms for each PT stratified by intensity, relationship and seriousness)
- Incidence of TEAEs (including all TEAEs during Treatment and Post-Treatment Periods) by SOC, HLT and PT and including the EAIR and EAER calculated as described in [Section 11.2.2](#)
- Incidence of TEAEs (including all TEAEs during Treatment and Post-Treatment Periods) by SOC, HLT and PT and including the EAIR and EAER, stratified by overall ADA status (positive/negative)

Has been changed to:-

In addition, the following summaries will be presented by treatment group (including All Subjects), SOC, high level term (HLT) and PT, based on the SS:

- Incidence of TEAEs during Treatment Period
- Incidence of TEAEs Overall

- Incidence of serious TEAEs during Treatment Period
- Incidence of serious TEAEs Overall
- Incidence of non-serious TEAEs during Treatment Period
- Incidence of non-serious TEAEs Overall
- Incidence of TEAEs during Treatment Period by relationship
- Incidence of TEAEs Overall by relationship
- Incidence of TEAEs during Treatment Period by maximum relationship
- Incidence of TEAEs Overall by maximum relationship
- Incidence of TEAEs during Treatment Period by maximum intensity
- Incidence of TEAEs Overall by maximum intensity
- Incidence of fatal TEAEs during Treatment Period by relationship
- Incidence of fatal TEAEs Overall by relationship
- Incidence of non-serious TEAEs during Treatment Period by relationship
- Incidence of non-serious TEAEs Overall by relationship
- Incidence of serious TEAEs during Treatment Period by relationship
- Incidence of serious TEAEs Overall by relationship
- Incidence of non-serious TEAEs during Treatment Period above threshold of 5% of subjects
- Incidence of non-serious TEAEs Overall above threshold of 5% of subjects
- Incidence of non-serious TEAEs during Treatment Period above threshold of 5% of subjects by relationship
- Incidence of non-serious TEAEs Overall above threshold of 5% of subjects by relationship
- Incidence of TEAEs during Treatment Period by SOC and PT (including the number and percentage of subjects and individual subject numbers/reported terms for each PT stratified by intensity, relationship and seriousness)
- Incidence of TEAEs (including all TEAEs during Treatment and Post-Treatment Periods) by SOC, HLT and PT and including the EAIR and EAER calculated as described in [Section 11.2.2](#)

Change #13: Section 14.6.1

- All serious TEAEs which code to a PT included in the Scope=Broad and/or Scope=Narrow groups of the following standardized MedDRA queries (SMQ):

Has been changed to:-

- All serious TEAEs which code to a PT included in the search=Broad scope of the following standardized MedDRA queries (SMQ):

Change #14: Section 14.6.1

- All serious TEAEs which code to a PT = ‘Cardiac failure congestive’

Has been changed to:-

- All serious TEAEs which code to a PT included in any of the following HLTs: “Heart Failures NEC”, “Left Ventricular Failures”, or “Right Ventricular Failures” and which also code to the SOC of “Cardiac Disorders” as the Primary SOC

Change #15: Section 14.6.4

Cytopenias will be tabulated separately based on the SMQ = ‘Haematopoietic cytopenias’. Only serious TEAEs will be included in the tabulation. The SMQ search should include all serious TEAEs which code to a PT included in the Scope=Broad and/or Scope=Narrow groups within the SMQ.

Has been changed to:-

Cytopenias will be tabulated separately based on the SMQ = ‘Haematopoietic cytopenias’. The SMQ search should include all TEAEs that code to a PT included in the Scope=Broad and/or Scope=Narrow groups within the SMQ.

Change #16: Section 14.6.6

Inflammatory bowel disease events will be tabulated separately, based on the HLT = ‘Colitis excl infective’.

Has been changed to:-

Inflammatory bowel disease events will be tabulated separately, based on the HLT = ‘Colitis excl infective’.

STATISTICAL ANALYSIS PLAN SIGNATURE PAGE

This document has been reviewed and approved per the Review and Approval of Clinical Documents Standard Operating Procedures. Signatures indicate that the final version of the SAP or amended SAP is released for execution.

PUBLIC COPY
This document cannot be used to support any marketing authorization application and any extensions or variations thereof.

PS0016 Statistical Analysis Plan Amendment 1

ELECTRONIC SIGNATURES

Signed by	Meaning of Signature	Server Approval Date (dd-mon-yyyy (HH:mm))
PPD	Subject Matter Expert Approval	30-Nov-2017 10:40 GMT+0
PPD	Clinical Approval	18-Dec-2017 12:14 GMT+01

This document cannot be used to support any application and any extensions or variations thereof.

PUBLIC COPY
Marketing authorization
